1. BACKGROUND

Stroke is one of the leading causes of disability in the UK and around the world.¹ In the UK there are around 100,000 strokes per year, increasingly occurring at an earlier age.² Advances in the medical management of stroke have reduced mortality but have had little impact on ongoing disability.³,⁴ Lower limb weakness is a common stroke-related impairment; around 41% of stroke survivors have lower limb weakness and 46% are unable to walk five days after stroke.⁵ As part of the normal ageing process older adults experience muscle wasting called sarcopenia, which can lead to a deterioration in muscle size and strength.⁶ Sarcopenia, along with stroke related muscle weakness, can contribute to a greater loss in muscle strength and function such as the ability to stand. Individuals who have lost independent functional movement post-stroke have limited ability to participate in exercises and activities to improve strength and function. ⁶ The inability to take part in active exercises can lead to a progressive cycle of limited movement which can contribute to further deterioration and poorer functional outcomes. Muscles and joints that are not moved or exercised are also at risk of developing joint contractures.^{8,9}

Active exercise can prevent deterioration in muscle size and function; ¹⁰ however, people with severe weakness have difficulty taking part. Emerging evidence suggests stimulating muscles with surface neuromuscular electrical stimulation (SNMES) can preserve and improve muscle size and strength in healthy adults ^{11,12} and in people after stroke.¹³ SNMES can increase type I & II muscle fibres, ^{14,15} muscle fibre diameter ¹⁶ and muscle size ¹⁷ which are associated with functional improvements in both healthy adults and stroke survivors. ¹⁶⁻²¹ However, most current SNMES protocols in stroke rehabilitation are aimed at helping muscles to activate during a functional activity ^{21,22} such as during reaching, walking, or cycling rather than maintaining muscle size and function. This suggests that the current protocols need refinement and extension to individuals unable to take part in active exercise due to muscle weakness.

This project builds on earlier research demonstrating the acceptability of using SNMES in unimpaired adults and people after stroke. SNMES was well-tolerated, with no reported adverse events. It is feasible to use in a clinical setting. Following SNMES, muscle size increased in people after stroke and unimpaired adults, along with spasticity reduction, increased activity and improved gait. This aligns with recent a review and NICE guideance indicating that, when used with functional activities, SNMES/FES (functional electrical stimulation) can improve weakness, coordination and spasticity, shoulder subluxation and walking/gait. The evidence is unequivocal that progressive strength training is beneficial after stroke. The updated 2023 National Clinical Guideline for Stroke recommends a minimum of 3 hours of therapist directed therapy per day and that people after stroke are active for 6 hours a day. This intervention will help contribute to those activity and rehabilitation goals. We are proposing to provide SNMES as a treatment for people who cannot actively engage in progressive strength training.

People with severe weakness after stroke who cannot participate in strengthening exercises will continue to have muscle wastage, making the muscles difficult to use when, and if, neuroplasticity (brain's ability to change in response to learning or rehabilitation) occurs. Using SNMES to prevent muscle wasting and maintain muscle size and function may help keep a muscle primed for when the individual is able to actively contract the muscle and participate in exercise and rehabilitation. The proposed SNMES protocol could contribute to an increase in rehabilitation input (minutes), inline with new Clinical Stroke Guidelines and provide a new intervention for people for whom there are few interventions available. Improving muscle size and function early after stroke may lead to an increased likelihood of

STIM-STROKE Protocol v1.0 30-04-2025

IRAS ID: 332116 Page **16** of **70**

return to functional mobility (standing, transferring and walking), improved function, and quality of life.

Aim: The aims of this feasibility study are to i. assess the feasibility and acceptability of SNMES started within 2 weeks after stroke and ii.to provide necessary data to inform the design of a future definitive RCT testing whether SNMES started within one week after stroke prevents muscle wastage and improves recovery of strength, walking and quality of life in people with severe lower extremity weakness.

1.1. Assessment and management of risk

Electrical stimulation is currently being used in routine care physiotherapy practice with minimal reports of adverse events. Electrical stimulation has been incorporated into best practice guidelines for people with stroke as well as people with Multiple Sclerosis. The risk associated with using electrical stimulation within this study is not different to using electrical stimulation within routine clinical practice.

Previous study of electrical stimulation report few adverse events. Common adverse events when they occur are skin irritation at the electrode site, muscle fatigue and soreness following electrical stimulation and joint pain.

Participants will be instructed to let the research team know if they experience any adverse events, these will be monitored as per Section 8 Safety Measures. If participants experience muscle soreness, muscle fatigue, joint pain, or skin irritation they will be supported by the research team to manage this to be able to continue in the study.

The benefits of using electrical stimulation are maintaining muscle bulk and size which will help to prevent atrophy, improved circulation at the stimulation site, and the time doing the stimulation will contribute to additional minutes of exercise which is recommended in the new Clinical Stroke Guidelines.

2. OBJECTIVES AND OUTCOME MEASURES/ENDPOINTS 2.1. Primary objective

The primary aims of this feasibility study are to i. assess the feasibility and acceptability of SNMES started within 2-weeks after stroke and applied for 12-weeks to the weakened lower limb muscles and ii.to provide necessary data to inform the design of a future definitive RCT testing whether SNMES started within two weeks after stroke prevents muscle wastage and improves recovery of strength, walking and quality of life in people with severe lower extremity weakness.

The primary feasibility and acceptability objectives are described below.

- 1. Determine the feasibility and acceptability of the SNMES intervention started within 2-weeks in people after stroke.
- 2. Estimate screening, recruitment and attrition rates, and reasons for declining participation or leaving the study early (where possible).
- 3. Estimate adherence/engagement to the SNMES protocol, including number of sessions completed/total sessions in treatment protocol

STIM-STROKE Protocol v1.0 30-04-2025

IRAS ID: 332116 Page **17** of **70**

- 4. Determine the acceptability of the outcome measures, data collection methods, and data completeness
- 5. Collect data to inform sample size for a definitive trial
- 6. Determine whether the protocol can be incorporated within routine clinical practice
- 7. Assess the feasibility of delivering SNMES in a range of settings eg. hospital, rehabilitation, home.
- 8. Determine if the participant sample is representative of the local areas of recruitment and of national stroke survivors to develop and implement an inclusive recruitment strategy for the next stage
- 9. Through the health economics component we will pilot data collection tools for resource use, will gather costs associated with delivering the intervention and will undertake an exploratory analysis of measured resource use and health-related quality of life. This will help inform the design of an economic evaluation for a future definitive trial including the perspective form which it should be carried out.
- 10. Pilot data collection tools to measure resource use in the follow-up period to inform the design of a future within-trial economic evaluation.

2.2. Secondary objectives

The secondary objectives of the study are the following:

- 1. Explore lower limb strength through dynamometer strength testing, functional testing such as the 30 Second Chair Sit-Stand Test, and the 10 Metre Walk test.
- Explore lower limb muscle bulk through limb circumference measurements, this will help the better understand muscle atrophy related to stroke, muscle weakness, and non-use.
- 3. Explore functional ability through the Barthel Index, 30 Second Chait Sit-Stand Test, and the 10 Metre Walk test.
- 4. Explore walking ability through the Barthel Index and the 10 Metre Walk test.
- 5. Explore sensation through the Nottingham Sensation Scale (tactile stimulation section only).
- 6. Explore quality of life through the EQ-5D-5L.
- 7. Explore health resource use through the health resource use questionnaire.

2.3. Outcome measures/endpoints

Feasibility and feasibility measurement

As this is a feasibility study the primary outcomes of interest relate to aspects of feasibility and acceptability. A red, amber, green (RAG) system will be used to identify if the feasibility study should progress to a definitive trial. Section 7.3 Statistical Analysis Plan specifies the RAG system in more detail. The aspects of feasibility and acceptability that will be explored are:

STIM-STROKE Protocol v1.0 30-04-2025

IRAS ID: 332116 Page **18** of **70**

- 1. Interviews with people with stroke and their caregivers as well as focus groups with clinicians to explore their experiences and views about the acceptability of the SNMES intervention. Furthermore exploring/tracking adverse events and adverse reactions to treatment with SNMES (a common side effect of electrical stimulation is skin irritation from the electrode pads) will contribute to the determining the feasibility and acceptability of the intervention.
- 2. Study enrolment rates and screening (the number of patients who agree to take part of those eligible). Where possible reasons for not taking part will be recorded to help plan the definitive trial. Additionally. data will be collected on the time duration between hospital admission and randomisation.
- 3. Through a participant diary, records within the electrical stimulation machine, and participant/caregiver interviews we will estimate engagement with the protocol and explore reasons for low or non-engagement with the protocol/not achieving recommended dose. This will help the team to identify if the suggested dose is feasible and acceptable on a larger scale.
- 4. Through participant/caregiver interviews, therapist focus groups, and completeness of collected data explore the feasibility and acceptability of the outcome measures used. Acceptability of candidate outcomes measures and their variability to inform the selection of outcomes, including the primary outcome, for a definitive trial, likely to be the 10-Metre Walk Test.
- 5. The data collected (including those from the outcome measures and participant interviews, data completeness, and standard deviation estimates) will inform the sample size considerations and primary outcome measure for the definitive trial.
- 6. Through participant/caregiver interviews and clinician focus groups explore the practicality of delivering the intervention in the proposed settings (such as the ability for people after stroke to carry out the SNMES intervention, if they need support, the level of caregiver or health care worker) support needed, and the ability to complete SNMES in a variety of settings. This will inform the methods of the definitive trial and if the stimulation protocol can be incorporated into routine practice.
- 7. Exploring the diversity of the recruited sample and estimating if this is representative of the wider population of people with stroke will help to inform the development and implementation of an inclusive recruitment strategy for the next stage (definitive trial).
- 8. Through the health economics and resource use questionnaire explore health resources used, costs of health resources, and costs of the interventions to inform the development of the health economics in the future trial.
- 9. (To meet aims 9 and 10) Pilot data collection tools to measure resource use in the follow-up period to inform the design of a future within-trial economic evaluation.

2.4. Feasibility Outcomes

The feasibility outcome will be explored at the end of the study. Feasibility data will be collected over the study period at Visit 1 (baseline), Visit 2 (6 weeks), Visit 3 (12-weeks) and Visit 4 (6 months). The final visit at 6 months will provide evidence of if there are any longer-term impacts of electrical stimulation on muscle size, strength, and function. Follow up at the 6-months timepoint is in line with recommendations by the Stroke Recovery Rehabilitation Roundtable as a key timepoint for assessment in stroke research and recovery.²⁶

The final analysis will help to inform and develop the definitive trial based on pre-specified RAG (red, amber, green) criteria described in Section 7.3 Statistical Analysis Plan.

STIM-STROKE Protocol v1.0 30-04-2025

IRAS ID: 332116 Page **19** of **70**

Table 1 – Table of Feasibility Outcome Collection

Objectives	Outcome Measures	Timepoint(s) of evaluation of this outcome measure (if applicable)
Primary Objective Assess the feasibility and acceptability of SNMES for 12-weeks to the weakened lower limb muscles started within 2 weeks after stroke. This will be achieved through the following: 1. Estimate screening, recruitment and attrition rates, and reasons for declining participation or leaving the study early (where possible).	1. Screening logs, recruitment, reasons for declining participation where give, and willingness to be randomised 2. Participant diary of stimulation sessions, data within the electrical stimulation unit, and participant/caregiver interviews 3. Participant/caregiver	 Screening, 6 week follow up, 12 week follow up, and 6 months follow up 6 weeks, and 12 weeks 6 weeks, 12 weeks, and 6 months Screening, 6 weeks, 12 weeks, and 6 months 6 weeks, and 12 weeks, 6 months 6 weeks, and 12 weeks, 6 months
2. Estimate adherence and engagement to the SNMES protocol, including number of sessions completed/total sessions in treatment protocol 3. Acceptability of the	interviews, therapist focus groups, completeness of collected data 4. Screening rates (reasons for declining), recruitment rates, attrition rates, outcome measures – 10 Metre Walk Test	7. 6 months8. 6 weeks, 12 weeks, 6 months9. 6 weeks, 12 weeks, and 6 months
outcome measures, data collection methods and data completeness 4. Collect data to inform sample size for a	 Therapist focus groups, participant/caregiver interviews, protocol engagement and adherence (diary and 	
definitive trial 5. Determine whether the protocol can be incorporated within routine clinical practice	data in electrical stimulation unit) 6. Participant and caregiver interviews, therapist focus groups, protocol	
 Assess the feasibility of delivering SNMES in a range of settings eg. hospital, rehabilitation, 	engagement and adherence across settings –diary and data in electrical stimulation unit	
home. 7. Determine if the participant sample is representative of the local areas of	7. Diversity of recruited participants compared to the local area and national statistics of people with stroke	

STIM-STROKE Protocol v1.0 30-04-2025

IRAS ID: 332116 Page **20** of **70**

recruitment and of national stroke survivors to develop and implement an inclusive recruitment strategy for the next stage 8. Identify, measure, and value resources required to deliver the SNMES intervention 9. Pilot data collection tools to measure resource use in the follow-up period to inform the design of a future within-trial economic evaluation.	8. Resource use questionnaire and therapist focus group 9. Resource use questionnaire	
Secondary Objective 1		
Lower limb strength	Dynamometer and MRC Grading	Baseline (visit 1) 6 weeks (Visit 2) 12 weeks (Visit 3) 6 months (Visit 4)
Secondary Objective 2		
Functional ability	Barthel Index 30 Second Sit-Stand Test 10 Metre Walk test (visit 3 and 4 only)	Baseline (visit 1) 6 weeks (Visit 2) 12 weeks (Visit 3) 6 months (Visit 4)
Secondary Objective 3		
	10 Metre Walk Test	12 weeks (Visit 3)
Walking ability		6 months (Visit 4)
Secondary Objective 4 Quality of Life	EQ-5D-5L	Baseline (visit 1) 6 weeks (Visit 2) 12 weeks (Visit 3) 6 months (Visit 4)
Secondary Objective 5	Tape measure to measure the	
Limb circumference	circumference of the thigh and calf	Baseline (visit 1) 6 weeks (Visit 2) 12 weeks (Visit 3) 6 months (Visit 4)
Secondary Objective 6 Pain in the stroke affected lower limb	Numerical Pain Rating Scale or the Pain Visual Analogue Scale to measure pain in the lower limb that is affected by the	Baseline (visit 1) 6 weeks (Visit 2) 12 weeks (Visit 3) 6 months (Visit 4)
	stroke.	o montrio (viole 4)

Page **21** of **70**

STIM-STROKE Protocol v1.0 30-04-2025

IRAS ID: 332116

Secondary Objective 7 Sensation in the lower limbs	Nottingham Sensory Assessment, Tactile Subscale only	Baseline (visit 1) 6 weeks (Visit 2) 12 weeks (Visit 3) 6 months (Visit 4)
Secondary Objective 8 Resource use	Resource use questionnaire	6 weeks (Visit 2) 12 weeks (Visit 3) 6 months (Visit 4)

IRAS ID: 332116 Page **22** of **70**

3. STUDY DESIGN

A parallel arm randomised controlled feasibility study with a nested qualitative and health economic component. A feasibility study is being used to explore recruitment, data collection methods, outcome measures, acceptability and feasibility of an SNMES protocol for people with leg weakness within 2 weeks after stroke.

This design will provide necessary data to inform the design of a future definitive RCT testing whether SNMES started within two weeks after stroke prevents muscle wastage and improves recovery of strength, walking and quality of life in people with severe lower extremity weakness.

The study design includes:

- 1. An RCT comparing a control group of usual care (n=30) versus an intervention group receiving usual care plus SNMES to the weakened leg muscles after stroke (n=30).
- 2. Nested qualitative component which includes:
 - a. Semi-structured interviews with participants with stroke, control group (n=8), intervention group (n=12).
 - b. Semi-structured interviews with caregivers to the participants in the SNMES intervention group (n=10)
 - c. Focus groups with clinicians who have helped to support the study and participants to use the SNMES (n=10).

4. STUDY SETTING

This is a multicentre study is across two acute trusts, University Hospitals Dorset (UHD) and a second site to be identified. The therapy teams at both sites will be supporting the intervention delivery. The therapy teams will be provided with an in-person training session of the electrical stimulation machines, troubleshooting, setup, removing electrodes at the end, and stimulation machine/electrode storage. The project manager will be available for support if needed.

4.1. Inclusion Criteria

The inclusion criteria for the participants with stroke are:

- 1. Adults ≥ 18 years of age within two-weeks of diagnosis of acute stroke
- 2. Sufficiently medically stable to participate in rehabilitation/trial interventions
- 3. National Institutes of Health Stroke Scale (NIHSS) score of ≥ 3 for the lower limb (limb weakness)
- 4. Unable to walk or transfer independently (with/without a walking aid)

Inclusion criteria for caregivers to people with stroke

1. Caregiver or family member to participant with stroke this is defined as:

An informal caregiver (hereafter referred to as caregivers) who is a family member or a close friend in a good relationship with the person with stroke. The caregiver will be older than 18 years of age, and able to communicate and assist the stroke survivor.

2. Participant with stroke they support was in the intervention group (SNMES)

STIM-STROKE Protocol v1.0 30-04-2025

IRAS ID: 332116 Page **23** of **70**

3. Caregiver or family member has the communication skills to be able to participate in an interview

Inclusion criteria for clinicians

- 1. Health care worker (e.g. but not limited to physiotherapist, occupational therapist, therapy technician/aid, nurse, healthcare assistant)
- 2. Supported the participants with stroke to use the SNMES during the study period

4.2. Exclusion Criteria

The exclusion criteria for the participants with stroke are:

- 1. Inability to gain informed consent from the patient or a consultee
- 2. Inability to walk independently prior to the stroke (with or without a walking aid)
- 3. Peripheral nerve injury to lower limb muscles
- 4. Pregnancy
- 5. Lower limb joint contractures
- 6. Contraindications to SNMES (DVT, uncontrolled epilepsy, malignancy at site of electrode placement, unstable fracture).
- 7. Poor skin condition and integrity at electrode sites (e.g. skin infection)
- 8. Previous stroke with residual lower limb weakness from first stroke
- 9. Impaired circulation in lower extremities
- 10. Additional underlying neurological condition e.g. Multiple Sclerosis or Parkinson's Disease
- 11. Cardiac pacemaker (the number of participants that have a cardiac pacemaker will be collected during screening, this will help to inform the development of the definitive trial and the inclusion and exclusion criteria)

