5.1. Participant Identification, Screening, and Recruitment

Participants with stroke

The recruitment strategy has been developed in collaboration with the Public Advisory Group (PAG).

Screening and recruitment will be from the acute stroke unit. Eligible participants will be identified through screening of all new and current stroke admissions to the trust. Screening will be completed by a research practitioner (RP); e.g. (but not limited to) research nurse (RN), or research physiotherapist (RPT) as well as clinicians working on the stroke units. The RP will screen new admissions of people with stroke against the eligibility criteria as well as attend ward rounds to facilitate identification of patients that meet the screening/eligibility criteria. Clinical teams that identify someone that meets the eligibility criteria will notify the research team and research practitioners. At both sites, either clinicians in the therapy team or research staff involved in screening are employed by the participating site's R&D team (e.g. research nurses or research physios) routinely have access to patient data as part of their role.

When a RP identifies a patient with stroke who meets the eligibility criteria, they will provide the patient with the participant information sheet. If it is unclear from the chart or ward rounds if the patient is eligible, the RP will refer to the treating therapist to confirm the person with stroke meets the eligibility criteria (e.g. strength and walking ability) prior to providing the participant information sheet.

A detailed screening log will be kept detailing stroke admissions, those meeting the screening eligibility criteria, those that do not meet the criteria and why (which criteria they do not meet), those approached about the study, and reasons for declining if the participant is willing to provide a reason, they do not have to.

If a patient is screened and is meets all eligibility criteria except they are not medically or neurologically stable, they will continue to remain on the screening log and checked on for

STIM-STROKE Protocol v1.0 30-04-2025

IRAS ID: 332116 Page **29** of **70**

10 days. If at 10 days the patient is medically/neurologically stable and meets all inclusion criteria they will be provided information about the study, if they do not meet the eligibility criteria then they will be excluded.

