5.2.1.1 Consent for participants with stroke deemed to not have capacity

Following stroke, is it likely that a proportion of potential participants will be unable to independently make a decision about taking part in the trial (i.e. lack capacity), but otherwise meet the inclusion criteria. This is particularly relevant in the early phase following stroke, where capacity may be borderline or fluctuating, but the person is otherwise engaging in their rehabilitation. For example, an individual may be able to understand the general nature of the research and what participation would involve but may not fully understand that their data will be used for a research study.

To maintain relevance and ensure generalisability of the findings, it is important to be inclusive when inviting people to take part, additionally the PPI group felt all patients should be given the opportunity to take part. The trial will therefore include participants who do not have capacity to consent to participation. This is deemed appropriate given that:

- Risks associated with the study intervention are negligible
- Electrical stimulation is used in routine physiotherapy practice; we are using it in a new and different way

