Process for gaining a consultee declaration for the participant with stroke

If a potential participant is deemed unable to consent to the study (i.e. they lack capacity), then a personal consultee (usually the next of kin or close friend/relative) will be asked to consider whether they would be willing to provide consent on their behalf, based on the presumed wishes of the potential participant. The personal consultee will be identified through collaboration with the clinical team working with the person with stroke.

The full version of the Consultee Participant Information Sheet will be shared with the identified consultee as well as the Easy Read PIS, or video PIS if requested. If the consultee feels that joining the study would be something the person with stroke would want to do, they will be asked to sign the consultee declaration form, on behalf of their relative/friend.

In the event that a personal consultee cannot be found for someone who is deemed to lack capacity, the person lacking capacity would not be able to participate in the study.

At all times, the wishes of the participant will be upheld. If the participant does not want to continue with the study, they are able to withdraw at any time without giving a reason. Leaving the study will have no impact on their usual rehabilitation or medical care.

Process if a participant with stroke gains capacity during the study

It is feasible that a participant who did not have capacity to provide informed consent at the beginning of the study, regains the ability to do so at some point during the study. The therapists who are delivering the treatment interventions, as well as the research team, will be briefed with regards to this. The participant's mental capacity will be reassessed. If, at this point, the person is deemed to have capacity to make a decision regarding participation in the research, they will be provided with the study information (PIS in the format of their choice) and will be supported to make this decision. If they opt to withdraw from the study, they can do so, without consequence.

Therefore, the Consultee Declaration only applies for as long as the participant lacks capacity. Data collected up to this point will be included in the final analysis, unless the individual explicitly asks for it not to be.

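### Exclusion 1 makes failure to obtain consent or a consultee declaration an eligibility matter, so uptake among those eligible may be overstated

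*Protocol*

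**What the plan says.** The first exclusion criterion for participants with stroke (section 4.2) is "Inability to gain informed consent from the patient or a consultee". It stands in the same list as the clinical exclusions.

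Section 2.3, like the trial summary, defines the enrolment rate as "the number of patients who agree to take part of those eligible". Estimating recruitment is one of the primary feasibility objectives (section 2.1). Precision of the uptake estimate is part of the sample size justification (section 7.1).

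Section 5.1 has the research practitioner confirm eligibility first and then give the information sheet. Section 5.2.1 then allows at least 24 hours before consent. The screening log is to record "those that do not meet the criteria and why (which criteria they do not meet"; it also records, as separate items, who was approached and any reasons given for declining.

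On capacity, section 5.2.1.1 expects some patients to be "unable to independently make a decision about taking part in the trial (i.e. lack capacity), but otherwise meet the inclusion criteria". Under the consultee heading in section 5.2.1.2, where "a personal consultee cannot be found for someone who is deemed to lack capacity", the rule is that "the person lacking capacity would not be able to participate in the study".

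**The concern.** A criterion that can be known only after consent has been sought cannot form part of an eligibility judgement made before it. The consent sections treat a person lacking capacity as otherwise eligible, and they say that a person with no consultee cannot take part. They do not say whether that person counts as ineligible or as eligible but not recruited. The exclusion list is the only place that answers, and it answers *excluded*.

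That answer reaches a reported outcome. Uptake has those eligible as its denominator, and removing people who did not enter from a denominator can only raise the rate. The group is not incidental. The trial takes people with severe leg weakness within two weeks of stroke, the protocol expects impaired capacity among them, and only a personal consultee is allowed for. How many patients are lost on that route is something a feasibility study should show when the definitive trial is planned.

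**Working it through.** **Inputs from the protocol**
- Target sample: 60 (section 7.1).
- Patients at one site in one year with a lower limb score of 3 or 4: 298 (section 7.2).
- Share of these expected to be eligible: about 50% (section 7.2).
- Expected number approached: around 149 (section 7.2).
- Planned margin for uptake: 10 points, 90% two-sided or 95% one-sided (section 7.1).

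**Assumption**
- f is the share of clinically eligible patients coded under exclusion 1 because no consultee could be found, or because the consultee declined. The protocol gives neither the share lacking capacity nor the share without a consultee, so f is varied from 5% to 30%.

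**Step 1: reproduce the planned denominator.** 298 × 0.50 = 149, as stated. No consent filter enters this figure, so it can stand in for the clinically eligible. Uptake with all of them in the denominator is 60/149 = 40.3%.

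**Step 2: sampling margin at that denominator.** 1.645 × √(0.403 × 0.597 / 149) = 0.066, or 6.6 points, inside the planned 10.

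**Step 3: uptake when a share f is removed.** U(f) = 60 / [149 × (1 − f)].

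| f (assumed) | Denominator | Uptake | Excess over 40.3% |
|---|---|---|---|
| 0% | 149.0 | 40.3% | none |
| 5% | 141.6 | 42.4% | 2.1 points |
| 10% | 134.1 | 44.7% | 4.5 points |
| 20% | 119.2 | 50.3% | 10.1 points |
| 30% | 104.3 | 57.5% | 17.3 points |

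**Step 4: when does the bias equal the planned margin?** Set U(f) = 0.4027 + 0.10. Then f = 1 − 0.4027/0.5027 = 0.199, about 20%.

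**Step 5: dependence on the denominator.** The relative inflation is 1/(1 − f) whatever the denominator: 1.05 at 5%, 1.11 at 10%, 1.25 at 20% and 1.43 at 30%. The excess in points does depend on it. Section 7.2 also says that 35% of about 2000 admissions are likely to be eligible, which is 700. On that base uptake is 60/700 = 8.6%. With f = 20% it is 60/560 = 10.7%, an excess of 2.1 points rather than 10.1.

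**The case against.** The best defence is that the protocol's working sequence already fixes eligibility before consent. A research practitioner following section 5.1 would count a patient as eligible on giving out the information sheet, and later failure to find a consultee would not undo that. This stands in part: the overstatement is conditional on exclusion 1 being applied as written. It does not remove the conflict, because the criterion is in the list and staff are entitled to apply it.

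Second, the log records which criterion each excluded patient failed. Those coded under exclusion 1 can therefore be counted and the rate over all clinically eligible patients recovered. This largely stands, provided coding is consistent. A consultee's refusal fits both exclusion 1 and the log's declining category, and the trial flow chart sends ineligible and declining patients to the same exit box.

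Third, the exact uptake denominator might be left to a statistical analysis plan, which is not to hand. But the criterion itself is stated in the protocol and operates during recruitment. A later plan cannot separate cases that the log has merged.

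A reader might also infer three stronger things, none of which the protocol supports:
- *Every patient from whom consent was not gained, including those with capacity who say no, becomes ineligible, so that uptake would be complete by construction.* Section 5.1 logs declining separately from failing a criterion. The definition in section 2.3 makes sense only if decliners are eligible.
- *The assessment of how representative the sample is would be biased.* Table 1 compares recruited participants with local and national statistics, and the eligible denominator plays no part in that.
- *The progression decision would be affected.* Table 3 judges recruitment by the number recruited (50 or more, 30 to 49, fewer than 30), not by a rate.

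**Conclusion.** The point holds in a limited form. Exclusion 1 conflicts with the protocol's own order of steps and with its description of people lacking capacity. Applied as written, it removes patients who lack capacity and have no personal consultee from the uptake denominator, and possibly those whose consultee declines.

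The direction is certain if that happens: uptake is overstated. The size is not known. On 60 recruits and 149 clinically eligible patients, an assumed 5% to 30% coded this way would move uptake from 40% to between about 42% and 58%. The excess would match the planned 10-point margin at about 20%. These figures rest on the assumed share and on using the expected number approached as the number clinically eligible.

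What is at stake is the reported uptake rate and the planning that draws on it. The change is worth making before recruitment because it is cheap and because inconsistent coding is hard to repair afterwards.

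**What to change.** - Take item 1 out of the exclusion list in section 4.2. State instead that consent or a consultee declaration is a condition of enrolment once eligibility is confirmed.
- Define the uptake denominator in section 2.3 and the trial summary as all patients meeting the clinical criteria before consent is sought.
- In the screening log, record three outcomes as eligible but not recruited: lacks capacity with no consultee found or reachable; consultee declined; patient declined.
- Report uptake over all clinically eligible patients.

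The cost is a change to protocol wording and log categories. Nobody's entry to the trial changes, because consent or a declaration is still required. Reported uptake may be lower than it would otherwise have been.
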